#### **IV. SUBJECT ENROLLMENT**

This is a nation-wide proof-of-concept randomized controlled trial conducted entirely remotely. We will enroll 225 nondaily smokers based on the following eligibility criteria: (a) 18+ years of age, (b) smartphone ownership (Android or iPhone only) (c) current nondaily smoker, who smokes at least weekly, and no more than 25 out of the past 30 days, and (d) lifetime history of having smoked 100+ cigarettes, and (e) is willing to make a smoking quit attempt as part of this study.

Participants will participate in screening, consisting of (1) a phone screen, (2) an online screening survey, which will contain check-questions to verify that respondents are truly reading items (100% accuracy required; If less than 100% accuracy, participant is screened out unless there is a compelling reason to justify missed check items. This would only happen upon review with the PI and after a phone conversation with the study participant has taken place to review the missed item(s) and explain the situation. Examples would include survey glitch, otherwise thoughtful write-in answer indicating survey attention, careful review of other survey answers and length of time spent on survey); (3) provision of contact information for two collaterals who can assist research staff in locating participants; collaterals will be told that the participant is participating in a study tracking health behaviors; and (4) provision of their social security number to enable remuneration by check, as required by MGH. We expect that 1/3 of participants who start the online survey will enroll in the study.

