(please see attached for the specific check items), staff will inform the screening participant that they are ineligible for the study. If the survey is complete and valid, staff will collect (via email, phone, and/or REDCap form) the contact information for collaterals the participant would like to specify for this study. Social security number (to enable payment by check) and a mailing address to which Accounts Payable can mail the check containing remuneration will be collected via phone, and only after participants have been enrolled in the study. For screen participants who do not enroll in the study (i.e., because they are ineligible or because they decide against the study) study staff will ask for verbal consent (via phone) to allow us to collect their SSN (during the same phone call) and send them a check for completing the screening survey.

At the end of this phone call, study staff will ask the screening participant to indicate the date on which they would like to quit smoking. The enrollment call is then scheduled to occur 8 days before that date. If the chosen quit date falls on a Monday or Sunday, meaning that the enrollment call should be on a Saturday or a Sunday, the enrollment call will be adjusted to fall on a weekday.

During the enrollment call, staff will review the study fact sheet with the participant, and will invite the participant to ask any questions they may have about the study and all its procedures. Once all questions have been answered, study staff will ask the participant to give verbal consent to enroll in this study. The date and time of this verbal consent will be documented by study staff in our REDCap dataset.

After providing verbal consent, the participant is randomized. This is an unblinded study. Randomization will occur via a randomization sheet, as generated using the PROC PLAN procedure in the statistical software package SAS. Randomization will be in a 1:1:1 ratio (SiS3 vs. QG vs. TAU), with a block size of 4. Study staff will use the randomization sheet to determine the participant's treatment group, document this randomized assignment in our REDCap dataset, and will then onboard the participant to the smoking cessation support they have been randomized to receive (i.e., our smartphone app SiS or NCI's app QuitGuide or TAU, which consists of NCI's written materials, "Clearing the Air"), using a time-matched, ~15 minute script.

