- Brief COPE, a 28-item scale designed to measure methods of coping with stress [e.g., “I’ve been getting emotional support from others.”] 4-point Likert: 1 = I haven’t been doing this at all, 2 = I’ve been doing this a little bit, 3 = I’ve been doing this a medium amount, 4 = I’ve been doing this a lot])

Participants will be remunerated according to the following remuneration schedule:

Table 2. Remuneration Schedule

Time Point	Survey*
Baseline & Screening	\$25
2-week	\$25
6-week	\$50
3-month	\$25
6-month	\$25
\$150 per participant	
* \$10 for a survey with missed check items	

Payment will be paid by check, where participants will receive a total of five checks, corresponding to the five study assessments occurring at screening, 2-week, 6-week, 3-month and 6-month follow-up. Participants will receive \$25 for each completed online survey, unless they fail to answer 100% of the randomly placed reading alertness check items correctly (e.g.: "Please answer "not at all confident"."), in which case they receive \$10 for a given survey. (Correctly answering all check items is a screening criterion, which is explained to participants during the screening phone call). At the primary endpoint, the 6-week assessment, participants receive an additional \$25 for the survey, because this survey is longer than the other surveys.

Risks are expected to be minimal, and include breach of confidentiality, subject discomfort from answering questions about smoking, and discomfort from quitting smoking. We will minimize these risks by safeguarding electronic data capture by using HIPAA-compliant electronic data capture processes, assuring participants that they do not need to answer any questions they do not want to answer, and by providing information on how to manage smoking cessation.

A subject will be removed from the study if he or she no longer wishes to participate for any reason. A subject may also be removed from the study by the PI, if the participant cannot comply with study procedures (e.g., responds incorrectly to survey check items, cannot install the app on his/her smartphone) or causes undue distress to study staff (e.g., becomes belligerent towards study staff).

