**Analytic Plan.** All successfully enrolled participants (i.e., passed the screening process, was successfully onboarded to the assigned smoking cessation materials) will be included in the outcome analyses. For hypotheses only relevant to the SiS and QG conditions (marked in Specific Aims), only participants successfully onboarded to those conditions will be included in the analyses.

1. **Primary Outcome (Aim 1).** In this proof-of-concept RCT, the primary outcome is self-efficacy to abstain from smoking, as measured by the SEQ-12. The primary endpoint is end-of-treatment, which occurs 6 weeks after the originally chosen quit day. To test for differences between randomized groups, we will fit a fixed effects repeated measures model using PROC MIXED, where observations are modeled as nested within persons. Predictors included in the model will be GROUP (i.e., SiS vs. QG vs. TAU), TIME (i.e., BL, Week 2, Week 6, Week 12 and Week 24), and the GROUP\*TIME interaction effect. A contrast statement will be used to derive the test statistic for the GROUP comparison at Week 6, our primary endpoint, given the overall longitudinal model. This contrast statement will test the null hypothesis that SiS = QG = TAU. If this null hypothesis is rejected ( $p<0.05$ ), we will conduct pair-wise follow-up tests that compare the three possible pairwise comparisons (i.e., SiS vs. QG, SiS vs. TAU, and QG vs. TAU).
2. **Secondary Outcomes (Aim 2).** The secondary outcomes in this proof-of-concept RCT are exploratory. Thus, we will not correct for multiple testing. We will fit one model per secondary outcome, using an alpha of 0.05 for all analyses.
  - 2.1. To test for differences between randomized groups for outcomes that are assessed multiple times (Aims 2a, 2b), our overall modeling approach will be the same as for Aim 1. That is, for each outcome, we will fit a fixed effects repeated measures model, where observations are modeled as nested within persons. Predictors included in the model will be GROUP, TIME, and the GROUP\*TIME interaction effect. However, for these secondary outcomes, the definitions of the TIME effect varies across these secondary outcomes, based on their assessment schedule. The distribution of the outcome variables also varies across these variables. Thus, we will implement this overall modeling approach for these variables as follows:

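### Randomised participants can be lost to the analysis through failed app installation, which can happen only in the two app arms, and through discretionary removal by an unblinded investigator

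*Combined protocol and SAP*

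**What the plan says.** Four parts of the combined protocol and SAP bear on this.

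- **Section V, after Table 2.** The removal rule is permissive: "A subject may also be removed from the study by the PI, if the participant cannot comply with study procedures". The examples given include a participant who "responds incorrectly to survey check items, cannot install the app on his/her smartphone". No threshold, timing or independent review is stated. The same part of section V sets another consequence for missed check items in a survey: "in which case they receive \$10 for a given survey". The footnote to Table 2 attaches the reduced payment to the survey column, which covers all five time points.
- **Section IV, order of events.** Consent is followed by randomisation, and only then do staff onboard the participant to the assigned support. The study is described as unblinded. TAU receives a written booklet.
- **Section IV, end of enrolment.** Enrolment stops when 225 people have been successfully onboarded, so the count is of people onboarded, not people randomised.
- **Section VI, Analytic Plan.** All successfully enrolled participants "will be included in the outcome analyses", and these are defined as people who "passed the screening process, was successfully onboarded to the assigned smoking cessation materials".

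No section says what happens to data from a removed participant, or whether a survey with failed check items is analysed.

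**The concern.** A randomised comparison is protected only if the people analysed in each arm are those allocated to it, or if losses do not depend on the arm. Failed installation breaks that condition by construction. It can be observed only after allocation, and only in SiS or QuitGuide. A TAU participant with the same phone and the same technical difficulty is walked through the booklet, counted as onboarded and analysed. If people who cannot install an app differ in their self-efficacy, the app arms lose them and TAU keeps them. Recruiting replacements restores the number but not the comparability.

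Failed check items raise a different issue. They can occur in any arm, so the rule itself does not favour one. But the decision to remove is discretionary, is taken by someone who can know the allocation, and can end follow-up before Week 6, the primary endpoint. Section IX has the same PI overseeing data collection and analysis.

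**Working it through.** **1. The plan's own figures.** Section VI gives d = 0.50, 64 per group, 85% retention, 75 enrolled per group and 225 in total. It does not state power or sidedness for the calculation; I assume 80% and two-sided 5%. The two-sample t-test then needs 63.77, so 64 per group (power 80.1%). Allowing for retention, 64/0.85 = 75.3, against 75 stated (75 × 0.85 = 63.75). The sample size reproduces apart from rounding. The point below concerns who is analysed, not this figure.

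**2. The rules side by side, for a randomised participant.**

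| Event | SiS or QuitGuide | TAU |
|---|---|---|
| Cannot install an app at onboarding | Not onboarded: outside the section VI set, not counted towards 225, open to removal under section V | Cannot arise |
| Misses check items in a follow-up survey | Reduced payment, possible removal | Same |
| Removed after onboarding | Within the section VI set; later surveys lost | Same |

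Only the first row depends on the arm by rule.

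**3. Size of the shift from the first row.** Let f be the share of an app arm excluded and g the amount, in SD, by which those excluded would score below those kept. The full-arm mean is (1 − f) × kept + f × excluded, so

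kept mean − full-arm mean = f × g.

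With no matching exclusion in TAU, the app versus TAU difference moves by f × g. The documents give neither f nor g; every value here is an assumption.

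| f | g = 0.25 | g = 0.5 | g = 1.0 |
|---|---|---|---|
| 2% | 0.005 | 0.010 | 0.020 |
| 5% | 0.013 | 0.025 | 0.050 |
| 10% | 0.025 | 0.050 | 0.100 |
| 15% | 0.037 | 0.075 | 0.150 |

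Against d = 0.50 the extremes are 0.005/0.50 = 1% and 0.15/0.50 = 30%. The sign follows from assuming that those excluded would score lower; if they would score higher, it reverses.

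**4. SiS versus QuitGuide.** The shift is f × g in SiS minus f × g in QuitGuide. It is zero if failure is alike for the two apps, and otherwise depends on how they differ.

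**5. Replacement.** With equal allocation, failure share f in each app arm and none in TAU, N randomised yield N(3 − 2f)/3 onboarded. Setting this to 225 gives N = 675/(3 − 2f): about 228, 233, 241 and 250 for f = 2%, 5%, 10% and 15%. At 15%, that is 250/3 = 83.3 onboarded in TAU and 0.85 × 83.3 = 70.8 in each app arm. The target is met while the arms drift apart, and the f × g shift remains.

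**6. Precision.** If instead the exclusions came after onboarding, without replacement and on top of the 15% loss, app versus TAU power at d = 0.50 would be 79.6%, 78.9%, 77.8% and 76.5% for the same four values of f. The power cost is small; bias is the issue.

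**The case against.** The strongest reply is that the plan is coherent. A reader might infer that removal for failed installation contradicts a rule that everyone is analysed. The documents do not support that: section VI limits the analysis to people screened and onboarded, so on failed installation sections IV, V and VI agree. This part of the reply stands, but it moves the problem rather than removing it. The arm-dependent condition sits in the definition of the analysis set and in the enrolment count, as well as in the removal rule.

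A reader might also infer that inattentive participants leave the app arms and stay in TAU. They need not: the check items are in surveys given to all arms. The reduced payment shows that such participants are expected to remain at least sometimes, and the removal sentence does not say when it applies. What is left is unblinded discretion and two unreconciled consequences for the same event.

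Third, removal from the study is not exclusion from the analysis. Someone removed after onboarding stays in the section VI set, and the repeated measures model can use the earlier surveys. That is fair, but a person removed before Week 6 has no observed primary endpoint.

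Fourth, one might add these losses to the planned 15%. The documents do not support that either: people who fail at onboarding are replaced, and nothing says that later removals fall outside the 85% retention assumption.

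Finally, installation failure may be rare, since eligibility already requires an Android phone or iPhone. That may be so, but the text describes no check before randomisation that the phone can run both apps. The phone screen script is an attachment not reproduced here and might contain one.

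**Conclusion.** The concern holds as a weakness in how the analysis set is formed. The main analysis is conditional on successful onboarding, an event after unblinded randomisation that failed installation can prevent in SiS and QuitGuide but not in TAU, and those who fail are replaced. It is therefore not an analysis of all randomised participants. For check items the finding is narrower: discretionary removal without blinding, and no stated handling of removed participants' data or of failed-check surveys.

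The size cannot be established from the documents. The 0.005 to 0.15 SD range is an illustration that rests on assumed exclusion of 2% to 15% in the app arm only and an assumed deficit of 0.25 to 1.0 SD. It applies to app versus TAU; SiS versus QuitGuide is affected only so far as failure differs between the apps. The bias is probably modest and does not invalidate the trial, but it is avoidable, and it cannot be repaired later if follow-up was never collected. The plan should be changed.

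**What to change.** - **Before randomisation (section IV):** confirm during screening that the participant's phone can run both apps.
- **Section V:** delete failed installation and failed check items as grounds for removing a randomised participant. Keep everyone on the survey schedule; the surveys run in REDCap and need neither app.
- **Sections IV and VI:** define the main analysis set as all randomised participants in their assigned arm, whether or not onboarded, and amend the enrolment count so that it no longer sets aside those who fail onboarding. Their baseline survey is already in hand because it is part of screening.
- **Reporting:** give the numbers randomised, onboarded and removed, by arm. State that data collected before any withdrawal are kept.
- **Failed-check surveys:** keep them in the main analysis and add a sensitivity analysis that excludes them. The reduced payment can stay.

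The cost is protocol wording and one screening question. The downside is that a few participants who were never onboarded and some lower-quality surveys stay in the main analysis, which may slightly dilute the effect.

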## VI. BIOSTATISTICAL ANALYSIS

**Statistical Power.** This is a proof-of-concept trial. Therefore, our primary endpoint is a process variable, a shorter-term variable that is linked to subsequent change on the outcome of ultimate interest. In this case, ultimately, the SiS app is hoped to have an effect on smoking cessation 6 months after the chosen quit day. Typically, effect sizes for mHealth interventions for smoking cessation are very small; their public health importance lies in their potential reach, where a small effect in a large population can make a considerable impact on public health. Specifically, for interventions delivered via websites, meta-analyses have reported an overall odds ratio for point prevalence abstinence of 1.14 [1.07-1.22], and Cohen's d=0.12. For text messaging, a Cochrane review estimated a relative risk of 1.54 [1.19-2.00] in favor of automated text messaging interventions compared to minimal smoking cessation support. Such effect sizes require large scale RCTs, which is beyond the scope of this proof-of-concept RCT. Thus, as a process indicator of subsequent smoking cessation, we have selected self-efficacy to abstain from smoking as our primary outcome variable, because self-efficacy has been identified as the primary mediator by which a text-messaging intervention conferred smoking cessation benefit. Similar to our study, this trial used the "Clearing the Air" booklet as the control condition, and

showed that self-efficacy observed one month after the chosen quit day mediated group differences in smoking cessation at the 6-month follow-up.

In selecting the sample size for this proof-of-concept trial, we were guided by the effect observed in that text-messaging trial. Namely, in the text-messaging study, the observed group difference between treatment and control at 1 month post quit day on self-efficacy was  $d=0.66$ . Thus, we conservatively powered our proof-of-concept RCT to detect an effect size of  $d=0.50$ . Using SAS PROC POWER, we calculated that we would need a sample size of  $n=64$  per group to detect an effect of  $d\geq0.50$ . Assuming a retention rate of 85%, we would need to enroll  $n=75$  per group in order to retain  $n=64$  by end of treatment. Thus, the total number of participants to be enrolled into this trial is  $n=225$  (3 randomized groups \* 75 participants to be enrolled in each group = 225).

**Analytic Plan.** All successfully enrolled participants (i.e., passed the screening process, was successfully onboarded to the assigned smoking cessation materials) will be included in the outcome analyses. For hypotheses only relevant to the SiS and QG conditions (marked in Specific Aims), only participants successfully onboarded to those conditions will be included in the analyses.

1. **Primary Outcome (Aim 1).** In this proof-of-concept RCT, the primary outcome is self-efficacy to abstain from smoking, as measured by the SEQ-12. The primary endpoint is end-of-treatment, which occurs 6 weeks after the originally chosen quit day. To test for differences between randomized groups, we will fit a fixed effects repeated measures model using PROC MIXED, where observations are modeled as nested within persons. Predictors included in the model will be GROUP (i.e., SiS vs. QG vs. TAU), TIME (i.e., BL, Week 2, Week 6, Week 12 and Week 24), and the GROUP\*TIME interaction effect. A contrast statement will be used to derive the test statistic for the GROUP comparison at Week 6, our primary endpoint, given the overall longitudinal model. This contrast statement will test the null hypothesis that SiS = QG = TAU. If this null hypothesis is rejected ( $p<0.05$ ), we will conduct pair-wise follow-up tests that compare the three possible pairwise comparisons (i.e., SiS vs. QG, SiS vs. TAU, and QG vs. TAU).
2. **Secondary Outcomes (Aim 2).** The secondary outcomes in this proof-of-concept RCT are exploratory. Thus, we will not correct for multiple testing. We will fit one model per secondary outcome, using an alpha of 0.05 for all analyses.
  - 2.1. To test for differences between randomized groups for outcomes that are assessed multiple times (Aims 2a, 2b), our overall modeling approach will be the same as for Aim 1. That is, for each outcome, we will fit a fixed effects repeated measures model, where observations are modeled as nested within persons. Predictors included in the model will be GROUP, TIME, and the GROUP\*TIME interaction effect. However, for these secondary outcomes, the definitions of the TIME effect varies across these secondary outcomes, based on their assessment schedule. The distribution of the outcome variables also varies across these variables. Thus, we will implement this overall modeling approach for these variables as follows:
    - 2.1.1. (Aim 2a) Self-reported 30-day point-prevalence abstinence: the dependent variable will be a binary outcome variable (1=self-reported abstinence for 30 days, 0=not), which will be modeled over three timepoints (i.e., 6, 12 and 24 weeks post quit) using PROC GENMOD, where a binomial distribution with logit link function will be specified. The GROUP effect will include all three groups (SiS vs. QG vs.

TAU), as this outcome will be assessed in all randomized groups. Contrast statements will be used to derive the test statistics for the GROUP comparisons at Weeks 6, 12 and 24, given the overall longitudinal model. These contrast statements will test the null hypothesis that SiS = QG = TAU at the tested timepoints (i.e., Weeks 6, 12 and 24). If this null hypothesis is rejected ( $p<0.05$ ), we will conduct pair-wise follow-up tests that compare the three possible pairwise comparisons (i.e., SiS vs. QG, SiS vs. TAU, and QG vs. TAU).

2.1.2. (Aim 2b) Self-reported past week cigarette reduction: first, we will calculate reductions in cigarette consumption by subtracting the number of cigarettes smoked in the week leading up to the baseline assessment, as measured in the baseline survey, from the number of cigarettes smoked in the week leading up to the 2, 6, 12, and 24 week assessments, as assessed in these respective surveys. The resulting change score will be the dependent variable in the fixed effects repeated measures model, which will be modeled over four timepoints (i.e., 2, 6, 12 and 24 weeks post quit). We anticipate that this dependent variable will be normally distributed, but will also consider other possible distributions (e.g., Poisson). If normally distributed, this model will be fit in SAS using the PROC MIXED procedure. Contrast statements will be used to derive the test statistics for the GROUP comparisons at Weeks 2, 6, 12 and 24, given the overall longitudinal model. These contrast statements will test the null hypothesis that SiS = QG = TAU at the tested timepoints (i.e., Weeks 2, 6, 12 and 24). If this null hypothesis is rejected ( $p<0.05$ ), we will conduct pair-wise follow-up tests that compare the three possible pairwise comparisons (i.e., SiS vs. QG, SiS vs. TAU, and QG vs. TAU).

- 2.2. To test for differences between randomized groups for outcomes that are only assessed at end of treatment (Aims 2c – 2l), for each outcome, we will use a fixed effects model, where GROUP is the only predictor, and score at end of treatment is the dependent variable. Histograms will be used to guide selection of the most appropriate distribution. We anticipate that we will use the normal distribution for the CSQ-8 (Aim 2c), use of strategies (Aim 2e), perceived impact (Aim 2f), the AS (Aim 2g), actual app usage (Aim 2h), self-reported app usage (Aim 2i), likeability of the app (Aim 2j), satisfaction with the app (Aim 2k), and the SUS (Aim 2l), as implemented via the PROC MIXED procedure in SAS. We anticipate that we will use the Poisson distribution for time spent applying content (Aim 2d), as implemented via the PROC GENMOD procedure in SAS. If the GROUP effect is statistically significant ( $p<0.05$ ), we will conduct pair-wise follow-up tests that compare the three possible pairwise comparisons (i.e., SiS vs. QG, SiS vs. TAU, and QG vs. TAU). These follow-up analyses will not be necessary for secondary outcomes that are only assessed for the SiS and QG conditions (i.e., Aims 2j-2l).
3. Exploratory mediational models (Aim 3): We will use mediational modeling, using the product-of-coefficients approach and a fully lagged model to test if hypothesized within-person changes (see Figure 1) occur, and if they are linked to subsequent abstinence. The independent variable will be randomized group assignment (i.e., SiS vs. TAU), and the outcome variable will be self-reported 30-day point prevalence abstinence as measured at 6-month follow-up). The mediators will be our theorized mechanisms of change, as listed in the Aim 3 (i.e., self-efficacy, emotional well-being, desire to smoke, breadth of thought-action-repertoire, processing of processing of self-relevant health information.). Baseline values on these constructs will be included in the model to control for individual differences

on these measures. The mediator will be scale scores observed at mid-treatment, at the 2-week assessment, which marks the end of the cessation phase. We will use multiple mediation to determine the relative importance of each mechanism, and moderated multiple mediation to identify differences in mechanisms across subgroups (e.g., males vs. females, young adult vs. older adults), similarly to our approach in delineating mechanisms of behavior change in Alcoholics Anonymous.

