## II. SPECIFIC AIMS

This is the third study in a series of 3 studies to develop a smartphone app to support nondaily smokers in quitting smoking, as funded by the American Cancer Society grant #RSG CPPB – 130323 (project dates: 07/01/2017 – 6/30/2021). Study 1 (2017P001106) demonstrated feasibility and acceptability when smokers were onboarded in person. Study 2 (2018P002699) demonstrated feasibility and acceptability when smokers were onboarded remotely, nationwide. The present study is Study 3. It is a 3-group proof-of-concept RCT, in which we seek to test if our app (i.e., Version 3 of our developed smartphone app, called ‘Smiling instead of Smoking’ (SiS)) is superior to treatment as usual (i.e., TAU; no treatment for nondaily smokers) and superior to a control app (i.e., the National Cancer Institute’s smartphone app “QuitGuide” (QG). Specifically, our aims are to:

1. Test for differences between randomized groups on the primary outcome of this proof-of-concept RCT, as measured at end of treatment (i.e., Week 6 post-quit): Self-efficacy to remain abstinent, as measured via the Smoking Self-Efficacy Questionnaire (SEQ): two-dimensional 12-item self-report scale measuring a person’s confidence in his or her ability to abstain from smoking when facing internal stimuli [e.g. feeling depressed] and external stimuli [e.g. being with smokers]. Participants rate each item on a sliding scale from 0 [not at all confident] to 100 [extremely confident]. Two subscale scores are created by averaging items assessing internal vs. external stimuli, respectively. We hypothesize that SiS > QG > TAU.
2. Test for differences between randomized groups on secondary outcomes:
  - a. Self-reported 30-day point-prevalence abstinence 6, 12 and 24 weeks post quit. We hypothesize that SiS > QG > TAU.
  - b. Self-reported past week cigarette reduction at 2, 6, 12, and 24 weeks post quit, compared to baseline. We hypothesize that SiS > QG > TAU.
  - c. Satisfaction with smoking cessation support, as self-rated on the Client Satisfaction Questionnaire (CSQ-8) at end of treatment. We hypothesize that SiS > QG > TAU.
  - d. Time spent applying content brought up by the apps/”Clearing the Air” at end of treatment (“During this past week, how much time did you spend applying or contemplating the content of the SiS app/QG app/”Clearing the Air”?” [in minutes]). We hypothesize that SiS > QG > TAU.

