## **Control Condition #2: Treatment as Usual (TAU)**

Participants in the treatment as usual (TAU) condition will be asked to make a naturalistic quit attempt, using any methods they feel might help them. To time-match the onboarding experience of SiS and QG participants, study staff will use an onboarding script to lead TAU participants through the NCI booklet “Clearing the Air”, which encourages activities in the same order as implemented in the SiS behavioral challenges (i.e., reflecting on reasons to quit, informing about benefits of quitting, logging smoking and its triggers, formulating strategies for dealing with triggers). Additionally, “Clearing the Air” provides information on smoking cessation support resources, such as counseling and pharmacological approaches.

At the end of treatment, participants complete an online survey via REDCap. This is our primary study endpoint (see Specific Aims). Participants complete two more online surveys via REDCap, occurring 12 and 24 weeks post-quit, for secondary aims.

Table 1 specifies which data are collected at which time points. Please see attached for specific descriptions of each of these measures.

Table 1. Data Collection Instruments per Time Point

Type of Measure Specific Measure	Timing of Assessment				
	BL	Wk 2	Wk 6	Wk 12	Wk 24
Primary Outcome					
Smoking Self-Efficacy Questionnaire (SEQ-12)	X	X	X	X	X
Secondary outcomes					
Smoking status	X	X	X	X	X
Recent cigarette use	X	X	X	X	X
Client Satisfaction Questionnaire (CSQ-8)			X		
Time spent applying content			X	X	X
Use of smoking cessation strategies			X		
Perceived impact of SiS/QG/TAU on quitting			X		
Appreciation Scale (AS)			X		
(SiS/QG only) Actual app usage - continuously recorded	X	X	X	X	X
(SiS/QG only) Self-reported app usage: weeks -1 to 2		X			
(SiS/QG only) Self-reported app usage: weeks 3 to 6			X		
(SiS/QG only) App likeability & satisfaction			X		
(SiS/QG only) System Usability Scale (SUS)			X		
Other outcomes to be explored in mediational analyses					
Emotional well-being					
PANAS Positive And Negative Affect Schedule (PANAS)	X	X	X	X	X
Happiness single-item measures	X	X	X	X	X
Satisfaction With Life Scale (SWLS)	X	X	X	X	X
Subjective Happiness Scale (SHS)	X	X	X	X	X
Perceived Stress Scale (PSS10)	X	X	X	X	X
Desire to smoke					
Brief Questionnaire of Smoking Urges (QSU)	X	X	X	X	X
Thought action repertoire					
Modified Twenty Statement Test (mTST) - Baseline	X				

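### Does sizing the trial at 64 per group for d = 0.50, without naming the test or the pair of arms, leave the three-arm primary analysis underpowered?

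*Combined protocol and SAP*

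**What the plan says.** The sample size is set in Section VI, Statistical Power. A text-messaging trial with a self-efficacy difference of d = 0.66 is the guide, and the plan scales down from it: "Thus, we conservatively powered our proof-of-concept RCT to detect an effect size of" 0.50. The calculation is given in one sentence: "Using SAS PROC POWER, we calculated that we would need a sample size of" 64 per group. "Assuming a retention rate of 85" per cent, that becomes 75 enrolled per group and 225 in all. The source trial had the NCI "booklet as the control condition". The same booklet is the TAU material here, since under Control Condition #2 "study staff will use an onboarding script to lead TAU participants through the NCI booklet".

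The test is set in Section VI, Analytic Plan, item 1: "we will fit a fixed effects repeated measures model using PROC MIXED", with group, time and their interaction over five assessments. At Week 6, "This contrast statement will test the null hypothesis that SiS = QG = TAU". Pairwise comparisons follow only if p < 0.05.

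Section II, Specific Aims, seeks to show that SiS is superior to TAU "and superior to a control app", and hypothesises the order SiS > QG > TAU.

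**The concern.** A reader who reproduces 64 will take it as 80% power for a two-arm comparison. The planned procedure is different: a 2-df test across three arms comes first and can block a pairwise difference that would have been significant alone. If the sizing ignored that step, power for SiS vs TAU would be lower than the reader supposes.

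The second worry is SiS vs QG, which is also a superiority aim. The 0.50 comes from a trial with a booklet control, so it reads most naturally as SiS–TAU. With QG hypothesised to lie above TAU, the SiS–QG difference would then be below 0.50, and no power is given for it. At stake would be an overstated chance of success for one aim and an unknown chance for the other.

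**Working it through.** **Inputs from the documents.** d = 0.50, 64 per group, 85% retention, 75 enrolled per group (Statistical Power); 1:1:1 allocation (Section IV); gate at p < 0.05 (Analytic Plan, item 1); order SiS > QG > TAU (Specific Aims).

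**Inputs assumed.** Two-sided 0.05 for the sizing and for each pairwise follow-up; one Week 6 score with SD 1; for the mixed model, compound symmetry with correlation 0.5 or 0.8, monotone dropout, and retention of 92%, 82% and 80% at Weeks 2, 12 and 24 (85% at Week 6 is the plan's own figure).

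**1. Reproduce the plan's figure.** Two-sample t-test with noncentrality d√(n/2):
- n = 64: 0.50 × √32 = 2.83, 126 df, power 80.1%.
- n = 63: power 79.5%.

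So 64 is the exact minimum for 80%. Enrolment: 64/0.85 = 75.3, and 75 × 0.85 = 63.75, so 75 is adequate to within rounding.

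**2. Power of the three-arm test at 64 per arm.** Noncentral F with 2 and 189 df, λ = n Σ(μᵢ − μ̄)², SiS–TAU = 0.50:
- QG equal to TAU or to SiS: λ = 64 × 0.1667 = 10.67, power 83.5%.
- QG midway: λ = 64 × 0.125 = 8.00, power 71.0%.

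To reach 80% this test needs 59 per arm in the first case and 79 in the second.

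**3. SiS vs TAU after the gate, reading 0.50 as SiS–TAU.** Simulation with 1,000,000 replicates and pooled three-arm variance, counting trials where the gate rejects and the pairwise test is significant in the right direction. Ranges run from QG midway to QG at either end.

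| Basis | After gate | Direct pairwise test |
|---|---|---|
| 64 completers per arm | 69.8–76.0% | 80.3% |
| Mixed model, correlation 0.5 (effective n 66.7) | 71.8–78.0% | 81.9% |
| Mixed model, correlation 0.8 (effective n 70.9) | 74.9–80.8% | 84.3% |

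Against the inferred 80%, the mixed-model range runs from 80 − 71.8 = 8.2 points below to 80.8 − 80 = 0.8 above. A loss of about 4 to 10 points appears only against the direct, unadjusted pairwise test, which the plan does not propose. A three-way Bonferroni split at 64 per arm (alpha 0.05/3) would have 65.6% power, less than the gate keeps. At the source trial's 0.66, power after the gate with 64 completers is 92–95%.

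**4. The other reading, 0.50 as SiS–QG.** With 64 per arm and QG 0, 0.10, 0.25 or 0.50 above TAU, SiS vs QG power after the gate is 76.1%, 78.6%, 80.1% and 80.4%. With QG 0.25 or more above TAU, SiS vs TAU exceeds 97%. The gate then costs almost nothing.

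**5. SiS vs QG when 0.50 is SiS–TAU, 64 per arm.**

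| QG above TAU | SiS–QG gap | Without gate | After gate |
|---|---|---|---|
| 0 | 0.50 | 80% | 76% |
| 0.125 | 0.375 | 56% | 53% |
| 0.25 | 0.25 | 29% | 28% |
| 0.375 | 0.125 | 10% | 10% |

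The two power columns fall together, so the decline comes from the size of the assumed gap and hardly at all from the gate. The documents give no value for QG's position.

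**The case for a change.** The strongest case for acting is that the omission is real and cheap to repair. The paragraph makes a formal power claim, the Analytic Plan makes a formal test, and the two are not tied together. The mixed model does not fully restore 80%: even with all 75 per arm observed at Week 6 and QG midway, SiS vs TAU after the gate is 77.4%. On the natural reading of 0.50, the hypothesised order forces the SiS–QG difference below 0.50, and the larger source-trial effect gives no assurance about that comparison. Calling the trial proof-of-concept does not excuse leaving the contrast unnamed.

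The omission stands as a reporting gap. What does not stand is the step from there to a fault in the design. The plan claims to detect 0.50 or more. It does not claim 80% power for SiS vs TAU after a three-arm test, nor any power for gaps of 0.25 or 0.125 between SiS and QG. A non-significant SiS vs QG result can still be read from its estimate and confidence interval, and nothing in the plan says it would be taken as equivalence.

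**Conclusion.** No change to the plan follows. The arithmetic behind 64 is sound, the gate is a valid way to order the comparisons, and 0.50 was set below the 0.66 seen in the source trial.

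A shortfall appears only if three unstated things are supplied: an 80% target, 0.50 meaning SiS–TAU, and a within-person correlation. With those, SiS vs TAU power after the gate is about 72–81% under the mixed model (correlation 0.5–0.8, assumed retention pattern), or 70–76% on 64 completers per arm. With 0.50 meaning SiS–QG, that comparison has about 76–80%. None of these figures would alter the number enrolled, the primary test or how its result is judged.

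Naming the contrast, test, alpha and power when the trial is reported would be good practice. The missing detail changes no result.
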